7.5.5.3. Analysis of TCN resistance in Syphilis cases

The analysis of TCN resistance in Syphilis cases will be conducted in all persons with an incident syphilis cases after baseline.

Outcome: Molecular TCN resistance will be defined as presence of mutations associated with TCN resistance in the CARD database.

Descriptive statistics: Tabulations of TCN resistance in Syphilis cases (TCN resistance testing missing, not resistant, resistant) will be reported at baseline, 3-, 6-, 9-, and 12-month visits in each arm.

Statistical analysis: Assessment of difference in prevalence of TCN resistance by arm across all post-baseline visits combined will be assessed by estimating the relative risk of TCN resistance using modified Poisson regression. The model will assess the relative risk of resistance by arm, adjusted for study site.

7.5.5.4. Analysis of TCN resistance in *S. aureus* carriers

The primary analysis of TCN resistance will be conducted in *S. aureus* cases detected at Baseline, 6- and 12-month visits.

Outcome: TCN resistance will be a dichotomous outcome defined as sensitive or resistance, based on e-Test cut-offs.

Descriptive statistics: Tabulations of TCN resistance in *S. aureus* cases (TCN resistance testing missing, not resistant, resistant) will be reported at baseline, 6- and 12-month visits in each arm. (site of *S. aureus*, if found, will not be known).

Statistical analysis: Assessment of difference in prevalence of TCN resistance by arm at each of 6 and 12 months will be assessed by estimating the relative risk of TCN resistance using modified Poisson regression. The model will assess the relative risk of resistance by arm, adjusted for study site at each time point. If an effect is found, assessment of a trend in time will be assessed by fitting a linear trend over study time. If prevalence of resistance is < 5%, analysis will pool across visits.

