3 OBJECTIVES

3.1 Primary Objectives

- 3.1.1 Evaluate the effectiveness of doxycycline post-exposure prophylaxis (PEP) to reduce STI infections in two populations: a) MSM/TGW living with HIV and b) MSM/TGW taking HIV PrEP.
- 3.1.2 Investigate the impact of doxycycline PEP on development of culture-based tetracycline (TCN) resistance in *N. gonorrheae* and among nasopharyngeal carriers of *S. aureus*

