10.5 Analyses after 5/13/2022 closure to enrollment

Analyses after 5/13/2022 closure to enrollment and doxycycline provision to control will include the following:

STI incidence:

- Comparison of STI incidence per quarter in control arm before and after doxycycline initiation
- Comparison of STI incidence per quarter in all participants receiving doxycycline (including those in control arm after rolled over to receive doxycycline) compared to incidence on control arm prior to doxycycline roll over

Antimicrobial resistance

- Evaluation of tetracycline resistance in *Staphylococcus aureus*, commensal *Neisseria* in comparison to the control arm and to individual baseline
- Evaluation of genotypic or phenotypic tetracycline resistance in bacterial STIs in all participants who receive doxycycline compared to control arm participants, prior to receipt of doxycycline.
- Evaluation of changes in the gut microbiome and total gut burden of tetracycline resistance before and after taking doxycycline PEP

Adherence

- Evaluation of doxycycline coverage of qualifying sex before and after study closure 5/13/2022

Acceptability

- Proportion of control arm participants who opt to take study provided doxycycline. Control arm participants who terminate study participation will have the reason for termination recorded to determine if stopping to receive doxycycline outside of the study.

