2.2.1.2. Impact of doxycycline on TCN resistance

1. Resistance of GC to TCN detected in positive GC cultures. Those with positive GC NAAT results will have a swab obtained from the involved anatomic site and other sites of sexual contact in past 90 days (to include throat, rectum, urine) for GC culture-based phenotypic testing. Swabs for GC culture will be collected at time of suspected GC or in patients recalled after positive GC NAAT result reported.
2. Tetracycline resistance detected in *S. aureus* culture-positive nasopharyngeal swabs, collected at baseline, six, and 12 months

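### The primary S. aureus resistance model leaves out the baseline result the trial collects and, unless prevalence is below 5%, tests months 6 and 12 separately with no named primary contrast, which costs precision

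*SAP*

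**What the plan says.** - **Objective.** Protocol 3.1 and SAP 2.1.1 set as a primary objective: "Investigate the impact of doxycycline PEP on development of culture-based tetracycline (TCN) resistance in" gonococcus and S. aureus carriers. SAP 2.2.1.2 makes resistance a primary endpoint in S. aureus "culture-positive nasopharyngeal swabs, collected at baseline, six, and 12 months".
- **Test.** SAP 7.5.5.4 plans "Assessment of difference in prevalence of TCN resistance by arm at each of 6 and 12 months", by modified Poisson regression. It continues: "The model will assess the relative risk of resistance by arm, adjusted for study site at each time point".
- **Baseline.** Resistance categories "will be reported at baseline, 6- and 12-month visits in each arm". This is a descriptive table. No baseline term appears in the model.
- **Conditional steps.** "If prevalence of resistance is < 5%, analysis will pool across visits". Also: "If an effect is found, assessment of a trend in time will be assessed by fitting a linear trend over study time". The section does not say which prevalence triggers pooling, or how repeated swabs from one participant are handled in either step.
- **Error control.** SAP 7.1 sets two-sided 0.05 for main effects, and SAP 7.4 plans no multiplicity adjustment. Neither visit is named as primary.
- **Later protocol text.** Protocol 10.5 (version 9.0) plans to evaluate S. aureus resistance "in comparison to the control arm and to individual baseline". The SAP is version 1.0, written for Protocol version 5.0, and has no such model.

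**The concern.** The objective speaks of resistance developing, and the trial cultures S. aureus before treatment. The only inferential model nevertheless treats a carrier who was resistant at entry the same as one who became resistant later. Within-person persistence of carriage and strain is what would make the baseline result informative, and the model does not use it.

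The two follow-up visits are also tested one at a time. Each test has only part of the follow-up information, and a significant result at either visit could be read as a positive finding. Carriers are a minority of participants, so precision is scarce. Protocol 1.2.8 gives antimicrobial resistance as one of the reasons for continuing follow-up after early closure.

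**Working it through.** **1. The plan's own figure.** The documents give no power, resistance rate or within-person correlation for S. aureus. Their power statement is for the STI endpoint: 246:123 evaluable per cohort, four visits, ICC 0.2, 10% against 5%. The effective control size is 123 × 4 / (1 + 3 × 0.2) = 307.5, with 615 on doxycycline. A pooled-variance test of two proportions gives 79.5% against the stated 80%. With ICC 0.1 it gives 86.6% against 87%. The same two-proportion formula is used in step 3.

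**2. Carriers per visit.** Two cohorts of 370 evaluable give 740, or 493:247 at 2:1. At about 30% carriage (Protocol 1.2.3) there are 740 × 0.30 = 222 carriers per visit, 148:74. With the 554 enrolled at the interim review (Protocol 1.2.8), the figure is 554 × 0.30 ≈ 166, about 111:55. Both cohorts are combined here.

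**3. Separate visits, no baseline term.** Let r be the effective correlation between a month-6 and a month-12 result (share of repeat carriers × their within-person correlation). One visit then holds (1 + r)/2 of the two-visit information. Illustrative power for assumed prevalences of 10% against 20% among carriers, one visit on n and two visits on 2n/(1 + r):

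| r | One visit's share | Two-visit power, 740 (one visit: 47%) | Two-visit power, 554 (one visit: 36%) |
|---|---|---|---|
| 0 | 50% | 78% | 65% |
| 0.2 | 60% | 70% | 56% |
| 0.5 | 75% | 60% | 47% |
| 0.8 | 90% | 51% | 40% |

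Two independent tests at 0.05 give a chance of at least one false positive of 1 − 0.95² = 9.75%. This falls to 9.6%, 9.1% and 7.8% if the test statistics correlate at 0.2, 0.5 and 0.8.

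**4. Adding the baseline result.** Simulation with 493:247 participants and 30% carriage. Assumed: 70% carriage persistence and 80% strain persistence per six months, and 10% of isolates resistant. There were 2,000–3,000 trials per setting.

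- SD of log RR with no effect: 0.492 at month 12 alone and 0.344 for one baseline-adjusted model over both visits. The variance ratio is 0.344² / 0.492² = 0.49.
- Power when resistance doubles only in newly acquired strains (a smaller effect than in step 3): 22.4% at month 12, 26.7% at either visit, 34.0% in the joint model. The Monte Carlo standard error at 34% is √(0.34 × 0.66 / 2000) ≈ 1 point.
- False positives at either visit: 6.9–8.0% for resistance of 10–15%.

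A repeat with 1,000 trials per setting gave SDs of 0.48 (month 12), 0.41 (both visits, clustered, no baseline) and 0.34 (both visits with baseline). Joining the visits therefore leaves 0.41² / 0.48² = 0.73 of the variance, and adding baseline leaves 0.34² / 0.48² = 0.50. Power was 20%, 24% and 31.5%. False positives at either visit were 7.2–9.8%, and 4–6% for the joint model.

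**5. Fewer participants.** With 350:175, 10% resistance and the same doubling, power was 12% at month 12, 15% at either visit and 21% for the joint model.

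**The case against.** The strongest defence is that the planned comparison is valid. Randomization balances pre-existing resistance on average, so the arm contrast among carriers still addresses an effect of doxycycline. Baseline is tabulated by arm. Protocol 10.5 already plans an individual-baseline comparison, and SAP section 1 allows the plan to be updated before lock, so the mismatch may be version lag. The absence of multiplicity adjustment is stated openly. Averaging months 6 and 12 is itself a choice of estimand, and month 12 could be preferred if resistance accumulates. All of this stands. It makes the point one of efficiency and specification.

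Three stronger readings are tempting, and the documents do not support them:

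- A reader might infer that the contrast is confounded by resistance present at entry, or that baseline adjustment would isolate resistance that developed on treatment. Randomization answers the first. On the second, about 70% would be non-carriers at baseline, so a resistant strain found later cannot be classified, and any such model still conditions on carriage after randomization.
- A reader might infer that half the data are thrown away. Both visits are analysed. The roughly halved variance compares the joint model with month 12 alone under assumed persistence. For joining the visits alone, half is the limit at r = 0.
- A reader might infer that the pooling rule ignores repeated swabs, or pools the baseline visit. SAP 7.5.1 fits its modified Poisson model by GEE with robust errors, and the S. aureus test sentence names months 6 and 12. Unclustered pooling would be an inference from silence, so no inflated error rate is attributed to it.

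**Conclusion.** The point holds as a loss of precision and a gap in specification. It is not a bias. The model omits a baseline result already collected, does not deliver the individual-baseline comparison in Protocol 10.5, and above 5% prevalence leaves two unadjusted tests with no primary contrast.

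Under the stated assumptions the SD of log RR falls from about 0.49 (month 12 alone) to about 0.34. The fair power comparison sets either visit against the joint model: about 27% with 7–8% false positives, against about 34% at about 5%. Comparing month 12 alone (22%) with 34% would overstate the gain, because the plan tests both visits.

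Only the carriage figure comes from the documents. The resistance rate, effect size and both persistence rates are assumed, and the gain depends on within-person correlation. With the smaller number actually enrolled, every version has low power, so a better model would not by itself decide whether a real rise is detected. If the cohorts are analysed separately, each has about half the carriers.

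**What to change.** Replace the visit-by-visit models in SAP 7.5.5.4 with one modified Poisson GEE over months 6 and 12, clustered by participant with robust standard errors. Covariates: arm, visit, site, and baseline status in three levels (not a carrier, susceptible, resistant). Then state:

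- one primary arm contrast, named in advance (for example the effect averaged over both visits), with visit-specific estimates from an arm-by-visit term as secondary;
- that the baseline visit is a covariate and never an outcome, since the section's opening sentence lists it among the visits analysed;
- that any pooling at low prevalence uses the same clustered model;
- how control-arm swabs taken after roll-over to doxycycline are handled. Protocol 10.5 limits the control comparison to time before doxycycline for the bacterial STIs but does not say so for S. aureus;
- that re-enrolled participants keep their original baseline swab. Under Protocol 6.8 they retain their assignment and repeat most day-0 evaluations, so a second baseline may follow doxycycline exposure;
- that the estimate is resistance among current carriers and does not fully separate developed resistance from newly acquired resistant strains.

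The cost is SAP wording only. The cultures are already in the schedule.

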8. SAFETY AND TOLERABILITY

Statistical tests are not planned for adverse event comparisons between arms. Safety and tolerability will be assessed in the ITT cohort, or the doxycycline PEP arm only, given the open label nature of the cohorts.

8.1. Adverse Events and Deaths

8.1.1. AE Definitions

Only the following AEs are recorded on eCRFs:

- All grade 2 and higher hematologic and hepatic laboratory abnormalities.
- All SAEs.
- In those randomized to doxycycline PEP arm, all grade 3 and 4 AEs with attribution to doxycycline in the opinion of the site investigator.

8.1.2. Adverse Event Summary Tables

The number of Grade 2 and higher hematologic and hepatic AEs data will be tabulated by grade and arm. Subjects will be counted only once for each hematologic and hepatic report. For the doxycycline PEP arm, relatedness will be tabulated (see below of definition of relatedness).

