CBC and liver function tests*		$\sqrt{*}$		$\sqrt{*}$	$\sqrt{**}$		
HIV testing data from local care (HIV RNA, CD4)	\checkmark				\checkmark		

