6.3.20 ART and PrEP status

For PLWH, current ART regimen and status (taking vs. not taking) will be recorded at each visit. At entry and month 12 for PLWH, the most recent HIV RNA and CD4⁺ cell count available from clinical visits will be recorded if available

For participants on PrEP At each visit for those on PrEP, PrEP status will be assessed (taking vs. not taking, and how PrEP is taken- daily vs intermittent). At entry and month 12, the most recent HIV antibody or viral load test results from clinical care will be recorded.

6.3.21 **Hematologic and liver function tests**: Complete blood count (CBC) (white count with differential, hemoglobin, platelets) and liver function testing (AST, ALT, total bilirubin and alkaline phosphatase)

will be drawn at months 3 and 9 in those on doxycycline PEP. Testing done through standard of care within 30 days of the study visit may also be used if available. For those in the standard of care arm, CBC will be done at the month 12 visit. In the event that a CBC cannot be obtained at month 12, an available CBC from any time during study participation may be used.

- 6.3.22 **Serum for storage** (Optional): At months 0 and 12, 10 mL of serum will be collected for storage for future analysis (non-genetic) in participants who agreed to this. Serum may be collected up to 14 days after the visit if blood cannot be collected at the time of the visit.
- 6.3.23 **Reimbursement**: Participants will be reimbursed at the enrollment visit, at quarterly visits, and at the time of return for treatment of STIs with accompanying collection of swabs. An additional reimbursement will be provided for participants who consent to the optional stool sample collection at the baseline, 6 month, and 12 month timepoints. No reimbursement will be provided at other unscheduled interim visits such as visits to provide additional doxycycline.

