3.5. Clinical Assessments

Safety assessments are limited to the following:

- All grade 2 and higher hematologic and hepatic laboratory abnormalities that are attributed to doxycycline in the opinion of the site investigator
- All AEs meeting SAE definition
- All grade 3 and 4 adverse events judged to be associated with doxycycline (possibly, probably or definitely related)

In this open label trial, for those randomized to receive doxycycline PEP, all AEs and SAEs have attribution recorded as doxycycline-related or not doxycycline-related, in the judgment of the site investigator.

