8.2. Laboratory Data

Laboratory data collected in this study consist of hematologic and liver function tests at months 3 and 9 in those on doxycycline PEP arm:

- Complete blood count (CBC) (white count, hemoglobin, platelets).
- Liver function testing (AST, ALT, total bilirubin and alkaline phosphatase)

The presentation of laboratory results focuses on the change from baseline to 3 and 9 months. All participants in the doxycycline PEP arm who have a baseline and at least one follow-up laboratory assessment, unless permanently discontinued doxycycline PEP, will be included in the presentation of the laboratory data. For each laboratory test, descriptive statistics will summarize the results at baseline, 3-, and 9-month assessment, and the change from baseline to 3- and 9-months assessments. The summary statistics are N, mean, s.d., median, and range. The within-group p-value from the paired t-test on the mean change from baseline and the 95% confidence interval limits for the mean change from baseline are also included with the change descriptive statistics. Figures will also be used to display change from baseline to 3 and 9 months.

The quantitative laboratory data for participants who have a baseline and follow-up laboratory assessment may be presented as scattergrams plotting the change from baseline as a function of the baseline value.

This analysis will omit values occurring after a participant has permanently discontinued study drug.

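### SAP 8.1.2 tabulates grade 2+ laboratory abnormalities by arm, but the arms are not tested on the same schedule, so the contrast is distorted or uninformative

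*SAP*

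**What the plan says.** **The table.** SAP 8.1.2: "The number of Grade 2 and higher hematologic and hepatic AEs data will be tabulated by grade and arm". The counting rule follows: "Subjects will be counted only once for each hematologic and hepatic report".

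**Testing on doxycycline.** SAP 8.2: "Laboratory data collected in this study consist of hematologic and liver function tests at months 3 and 9 in those on doxycycline PEP arm". Protocol 6.3.21 agrees that these tests "will be drawn at months 3 and 9 in those on doxycycline PEP".

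**Testing in controls.** The documents give three different answers.
- SAP 8.2 lists no control-arm laboratory test.
- Protocol 6.3.21: "For those in the standard of care arm, CBC will be done at the month 12 visit". It mentions no LFT for controls. If the month-12 CBC cannot be obtained, it accepts one from any other time on study.
- The Schedule of Events has a single row, "CBC and liver function tests", with intervention-only marks at months 3 and 9 and a standard-of-care-only mark at month 12. Read literally, controls get both panels once.

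**What is recorded.** SAP 8.1.1 lists "All grade 2 and higher hematologic and hepatic laboratory abnormalities" with no attribution filter, and SAP 2.2.2.2 agrees. SAP 3.5 is narrower: "All grade 2 and higher hematologic and hepatic laboratory abnormalities that are attributed to doxycycline in the opinion of the site investigator". Protocol 7.1 matches SAP 3.5.

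**The concern.** Most of these events come to light only when blood is drawn. If one arm is drawn twice and the other once or never, a count of participants with at least one abnormality partly measures how often each arm was tested.

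The control arm is the only concurrent reference for background abnormalities. Safety is a secondary objective, and a two-column table invites comparison. Background abnormalities could be read as doxycycline toxicity, and an empty control cell with no tests behind it could be read as a true zero.

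**Working it through.** The documents give no expected rate of grade 2+ abnormalities, so there is no planned figure to reproduce.

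**Inputs from the documents**
- Scheduled draws on doxycycline: 2 CBC and 2 LFT.
- Scheduled draws in controls off doxycycline: 0 or 1 CBC, and 0 or 1 LFT, depending on the section.
- Planned sample size 780 at 2:1, so 520 and 260.
- Protocol 1.2.8 reports 554 enrolled at the interim review. At 2:1 that is about 369 and 185.

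**Assumptions (not in the documents)**
- p, the chance of a grade 2+ abnormality at any one draw: same in both arms (no drug effect), range 0.5% to 5%.
- rho, the within-person correlation between two draws: 0 to 1.

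**Case A: all abnormalities are recorded (SAP 8.1.1, 2.2.2.2)**

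Chance of at least one abnormality in two draws:

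1 − [(1 − p)² + rho·p(1 − p)] = 2p − p² − rho·p(1 − p)

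With one control draw the chance is p. Dividing gives the expected risk ratio:

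RR = 2 − p − rho(1 − p)

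Hematologic events at p = 2%, 520 vs 260:

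| rho | RR | Doxycycline | Control, one CBC |
|---|---|---|---|
| 0 | 2 − 0.02 = 1.98 | 20.6 (4.0%) | 5.2 (2.0%) |
| 0.5 | 2 − 0.02 − 0.49 = 1.49 | 15.5 (3.0%) | 5.2 (2.0%) |
| 0.8 | 2 − 0.02 − 0.784 = 1.20 | 12.4 (2.4%) | 5.2 (2.0%) |
| 1 | 2 − 0.02 − 0.98 = 1.00 | 10.4 (2.0%) | 5.2 (2.0%) |

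- The choice of p hardly moves the ratio. At rho 0 it runs from 1.99 (p = 0.5%) to 1.95 (p = 5%).
- By exact binomials at p = 2%, the doxycycline percentage is the higher one with probability 0.94 at rho 0 and 0.78 at rho 0.5. With one test in each arm it is 0.48.
- Raw counts differ further because of the 2:1 allocation: 20.6/5.2 is about 4 to 1 at rho 0, and 15.5/5.2 about 3 to 1 at rho 0.5.
- With 369 and 185 participants the counts at p = 2% are 14.6 vs 3.7 (rho 0) and 11.0 vs 3.7 (rho 0.5). The ratios do not change.

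Hepatic events at p = 2%, 520 vs 260:
- If controls have no scheduled LFT (Protocol 6.3.21, SAP 8.2), expected counts from scheduled draws are between 20.6 vs 0 (rho 0) and 10.4 vs 0 (rho 1). The excess appears at any rho.
- If controls have one LFT (Schedule of Events), the hematologic table applies.

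**Case B: only abnormalities attributed to doxycycline are recorded (SAP 3.5, Protocol 7.1)**

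The model above does not apply. A control not taking doxycycline can hardly have an abnormality attributed to it, however often tested. The control column is then near zero by definition.

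**Check of the per-CBC comparison (Case A only)**

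At p = 2%, doxycycline has 2 × 520 = 1,040 CBCs with 20.8 expected abnormal, and controls have 260 with 5.2. Both are 2.0%, so the expected ratio is 1.00 at any rho.

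**The case against.** Several parts of the plan soften this.

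- *Denominators.* SAP 5.1 bases percentages on subjects with data, so untested controls should drop out of a percentage. That stands, but it does not correct two draws against one, and SAP 8.1.2 names a number.
- *No testing.* SAP section 8 plans no statistical tests of adverse events and allows assessment in the doxycycline arm alone. This limits the harm to presentation. SAP 8.1.2 nevertheless specifies a table by arm.
- *Relatedness.* SAP 8.1.2 also tabulates relatedness on doxycycline. That helps a careful reader, but the judgment is open-label and does not adjust the contrast.
- *Other sources of control results.* Protocol 1.2.1 describes liver tests and an annual CBC as typical care for people living with HIV. Under Protocol 6.3.24, controls who roll over have CBC and LFT at months 3 and 9, though those results are on drug. Neither document plans systematic capture of usual-care results in controls.
- *Versions.* The SAP follows Protocol 5.0, while the protocol at hand is 9.0. This may explain the disagreement about control labs, but the sections still need to be reconciled.

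A reader might infer that the table will double apparent toxicity. The documents do not support that: a ratio of about 2 is the upper end and needs independent draws. Persistent background abnormalities, such as those from chronic liver disease, would bring it towards 1. A reader might also infer that the control hepatic count is zero by design. That holds only for scheduled draws off doxycycline, and only if 6.3.21 governs.

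**Conclusion.** The point holds as a flaw in a descriptive safety table. On every reading of the schedule, doxycycline participants are tested more often than controls off doxycycline.

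Under the all-abnormalities rule, with no drug effect and one control CBC, the expected hematologic risk ratio lies between 1.0 and about 2, depending on an assumed rho. It is 1.0 only if abnormalities persist fully within a person. For hepatic events, scheduled testing gives controls no chance of an event if 6.3.21 governs. Under the attributed-only rule the contrast carries no information about background rates.

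It does not follow that the trial could draw a false-positive safety conclusion from a test, or that efficacy results are affected. No test is planned on this table, and the stopping boundaries in SAP 4.1 rest on the primary outcomes.

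**What to change.** In SAP 8.1.2:

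1. Show participants tested and tests done beside each cell, by panel and arm.
2. Show all doxycycline-arm abnormalities from months 3 and 9 descriptively. Make any between-arm hematologic comparison per CBC done, with abnormal CBCs as the numerator, using control CBCs taken before any roll-over to doxycycline. Do not reduce the doxycycline arm to its month-9 CBC: Protocol 8.1 has drug withheld for a related grade 3 toxicity, so a month-3 abnormality may have resolved by month 9 and would be lost.
3. Report hepatic abnormalities for the doxycycline arm only, with controls marked *not tested*, unless control LFTs were obtained.
4. Reconcile the Schedule of Events row with Protocol 6.3.21 on whether controls have LFT. Reconcile SAP 3.5 and Protocol 7.1 with SAP 8.1.1 and 2.2.2.2 on all versus attributed-only recording. A between-arm comparison is meaningful only under the all-abnormalities rule, so if the attributed-only rule governs, drop the control column.

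The cost is wording and some extra tabulation. The plan also gives up a simple per-participant count between arms.
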